Implementation of the DSMS at CDE-UNMH: The CDE-UNMH program uses the DSMS group education approach. Patients attend a six-week group instructional session with nine hours of class plus a one-on-one follow-up with a certified diabetes educator to provide individualized support by creating a customized education plan. The group sessions have discussion supported by didactic conversation "maps" where the facilitator guides but does not control the conversation based on session thematic goals. Patients then complete self-assessment forms. This format is the foundation of the DSMS Model for creating patient empowerment and program cultural competence.

Comparator #2.

The Chronic Care Model (CCM).^{31,44} The One Hope Centro de Vida Health Center Diabetes Program (One Hope) is based on the Chronic Care Model (CCM).^{31,44} The Chronic Care Model Framework: The CCM is "a systematic approach to restructuring medical care to create partnerships between health systems and communities"⁴⁴ by addressing not only the medical but also the cultural and linguistic needs of patients through the inclusion of cultural competence in the delivery system design.³¹ The CCM involves six synergistic domains: 1.) Improved access to care, 2.) Patient self-management support, 3.) Patient decision support, 4.) Care coordination, 5.) Integrated health information systems, and 6.) Access to community resources. The use of the CCM framework has been shown to yield significant results in the treatment of diabetes and is being used widely in chronic disease management.⁴⁵ To create a holistic care regime, the CCM focuses on addressing social determinants of health by meeting the medical, cultural, and linguistic needs of patients through integration of cultural norms and social relationships from the patient population into program design.³¹

Implementation of the CCM at One Hope: The One Hope program is designed to address the specific needs of Latino patients from low-income households^{32,33} by creating comprehensive, integrated, wrap-around services focused on culturally competent care.^{31,44} One Hope emphasizes Spanish as the language for service provision³³ and access to care

PROTOCOL TITLE: Comparing Program Options for Latinos with Diabetes

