regardless of ability to pay. The One Hope facility provides a physical environment that reflects the lifestyle and economic capacity of patients to make them feel comfortable and that they “belong” (in contrast to more clinical, corporate, or academic medical settings). One Hope is a community-run clinic with a director and staff who are members of the community and who are culturally and economically similar to the patients they serve, reducing the hierarchical power relationship that generally exists between patients and providers. This approach is evident in the way that doctors at One Hope share decision-making by engaging the patient and their family members in creating a plan for diabetes self-management.^{46,47} In addition, patients, caregivers and family members participate in a variety of program activities including cooking and nutrition workshops, zumba classes, and citas compartidas sessions (“shared appointments”).^{30,47-49} These shared appointment sessions allow patients, social supports and family members to share their stories and experiences in a peer support setting with facilitation by medically trained providers. But providers also “co-learn” from the patients.^{27,35,36} Through shared decision-making and shared appointments, providers learn about the realities of patients’ lives and their daily struggles at a level that goes beyond the interaction that normally occurs in a clinic. This helps the provider to be culturally competent by understanding diabetes from the perspective of the patient. Sharing experiences with peers and providers and including family members in activities offers a different level of social support for the patient by creating an enhanced feeling of intimacy and inclusion within the program. Innovative salidas (exit interviews), conducted routinely with all patients by a bilingual health navigator ensures that the patient understands and feels capable of implementing a doctor’s instructions, and integrates health system information by allowing the health navigator to communicate details of patient status back to the provider.³²

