3.0 Inclusion and Exclusion Criteria*

3.1 Describe how you individuals will be screened for eligibility.

Staff & Providers (n=36):

PROTOCOL TITLE: Comparing Program Options for Latinos with Diabetes

Our Program Liaison at each site will identify up to 6 key program staff and/or providers per site each year for assessment interviews that will contribute to our understanding of the program sites. Our Research Manager will contact them using an IRB-approved script to invite them to participate and schedule appointments with those interested. At the appointment, the Research Manager will ask them to sign the consent and complete the contact portion of the Data Sheet only, and then will conduct the interview.

Patient (n=240) & Social support (n=240) participants:

All patient participants will be individuals who have been identified by a provider as having pre-diabetes (A1c 5.7-6.4) or diabetes (A1c 6.5 or above) and are newly entering one of the two programs involved in this study (CDE-UNMH or One Hope). We will not enroll individuals who have already been participating at the sites as this would not allow us to gather data in line with our data collection protocol (baseline, 3, 6, and 12 months).

At CDE-UNMH, when patients register for the program, CDE-UNMH staff will tell them about the study using an IRB-approved script and a flyer with pull-off tabs will be posted in the CDE office. An invitation with further detail about the research and contact information for our PDCSs--the *Patient Data Collection Specialists* (PDCSs)--will be sent in a mailing that all new patients receive from CDE-UNMH with their class schedule confirmation and logistics. A staff person at CDE-UNMH or a member of the research team will phone new participants to tell them about the study. For those who indicate that they are interested, the staff person will ask the patient's permission to release their name and contact information to our PDCSs. If the patient agrees, a member of the research team will contact the patient. Interested patients can also contact the PDCS using the information on the mailing. For all interested patient participants, the PDCS will screen them per our recruitment criteria.

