At One Hope, participants will be identified in three ways: 1) New patients who call the clinic and indicate that they need to see a provider specifically about diabetes will be told about the study using an approved script, 2) Every patient seen at the clinic has an exit interview (*salida*) conducted by a Community Health Worker. For patients who have been told by their provider to have their A1c checked or that they have a diagnosis of diabetes or prediabetes, they will be told about the study using an approved script, and 3) Flyers about the study will be posted in the One Hope waiting room. For those who indicate interest in participating, a PDCS will contact them, inform them about the research per IRB requirements, and screen them for eligibility. For those who are eligible, the PDCS will schedule an appointment to consent them and gather baseline data.

PROTOCOL TITLE: Comparing Program Options for Latinos with Diabetes

At both sites, interested patients who qualify will provide contact information for a person that they identify from their social network (family or friend) whom they consider as their primary “social support.” A member of the research team will contact the social support, provide them with information about the study, and invite them to participate. The PDCS will schedule an appointment with supports who are interested.

At the appointment, the PDCS will ask all participants to sign the consent, collect the information in the Participant Data Sheet, and collect responses to the baseline survey questions. The PDCS will also obtain a blood sample, measure BMI, and gather a hair sample for the patient only.

Subset of Patient and Social support Participants for Interviews (72) and Focus Groups (72): At each of the sites, the PDCS will identify a convenience sample of interviewees and focus group participants from those already recruited to be in the study and invite them to participate. Our Research Manager will contact those interested to schedule.

3.2 *Describe the criteria that define who will be included or excluded in your final study sample.*

Staff & Providers will be individuals who work at one of the two sites.

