Eligibility Screening: potential participants who agree to being screened for eligibility will be contacted by a member of the research team and asked the eligibility screening questions, including requesting information about a potential social support partner. The patient participant will be offered the opportunity to contact their potential social support partner to inform him or her that a research team member will be in contact to conduct an eligibility screening. When the patient partner gives permission to contact the potential social support partner, a member of the research team will contact the potential social support partner and conduct the eligibility screening. If both the patient participant and his or her social support partner are deemed eligible, baseline data collection appointments will be scheduled with both participants. The information collected during the eligibility screening will be hand-written on an Eligibility Screening form and given to the Patient Engagement Coordinator, who will enter it into REDCap in the Eligibility Screening project. The Patient Engagement Coordinator will then create a record for the participant in the PCORI Diabetes Project in REDCap and assign a participant ID (PID) to the participant. The Patient Engagement Coordinator will keep a master list of the participants' names and PIDs both electronically and in hard copy. The electronic copy will be saved on her password-protected laptop, which is stored in a locked cabinet at One Hope when not in use. The hard copy will also be stored in a locked cabinet at One Hope.

Data Collection: at the baseline data collection appointment, the PDCS will collect and enter contact and demographic information into separate data collection instruments in the PCORI Diabetes Project in REDCap. At the baseline and all three follow-up appointments, the PDCSs will also administer the survey instrument to the participants, responses to which will be entered into a third data collection instrument in the same project. The PDCSs will also collect BMI measurements (weight and height) and draw blood for A1c testing at the baseline and all follow-up appointments and will collect a hair sample at the baseline and six-month follow-up appointment. The BMI measurements will be entered into a fourth data collection instrument in the PCORI Diabetes Project by the PDCS during

PROTOCOL TITLE: Comparing Program Options for Latinos with Diabetes

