Programmatic assessment. We will inventory each program regarding program design, size, structure, operation, and theoretical/philosophical orientation; professional qualifications/training of program providers; activities or resources available through the programs; strategies in place for Spanish language use or acceptance, inclusion of social supports and family, accommodation of challenges created by patients' limited socioeconomic circumstances, and the inclusion of stress management techniques; and data on referrals to the program, sign-ups, participation, no-shows, and attrition. We will conduct up to 36 interviews with key staff and/or providers (6/year x 2 sites x 3 years) to obtain their perspectives on implementation of the programs during the period of the study. Interview questions will be semi-structured to allow participants to contribute to the direction of the interview in relation to issues and ideas that they consider to be most relevant and important. Interviews will be audio-recorded and transcribed. We will assess patient and social support perceptions of the program interface using a cultural competence survey^{88,89} that asks about physician bias, inter-cultural understanding, respectful interactions, language barriers, experiences of discrimination, and issues of trust. Administration of the survey is described in the paragraph immediately below this one. The cultural competence portion of the survey will not be administered at baseline as the participant will not yet have experience with which to rate the program. To gather qualitative information, we will include questions on programmatic interface in interviews and focus groups with patients and social supports that are described two paragraphs below.

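### Study entry follows different program events at the two sites and baseline has no timing window, so the baseline-to-6-month changes are not assured to be comparable

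*Combined protocol and SAP*

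**What the plan says.** **Who may enter.** Section 3.1 limits the study to patients newly entering one of the two programs and adds an exclusion: "We will not enroll individuals who have already been participating at the sites as this would not allow us to gather data in line" with the baseline, 3-, 6- and 12-month schedule. Neither term is defined by visit or class.

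**When they are approached.** At CDE-UNMH, staff mention the study at registration, and an invitation goes out with the class schedule. At One Hope, Section 3.1 gives three routes: (1) new patients who telephone about diabetes, (2) the exit interview (salida) after a clinic visit, and (3) waiting-room flyers. Route 2 is for a defined group: "For patients who have been told by their provider to have their A1c checked or that they have a diagnosis of diabetes or prediabetes". Sections 23.1, 23.3 and 23.4 repeat this scheme.

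**What counts as the program.** Section 2.2 describes the One Hope program as including shared decision-making with the doctor and "Innovative salidas (exit interviews), conducted routinely with all patients by a bilingual health navigator". For CDE-UNMH it says: "Patients attend a six-week group instructional session with nine hours of class", followed by an individual session.

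**When baseline happens.** Section 9.2 (Surveys) equates baseline with entry to the study. Under Eligibility Screening it says: "If both the patient participant and his or her social support partner are deemed eligible, baseline data collection appointments will be scheduled with both participants". Under Programmatic assessment it leaves the cultural competence items out at baseline because "the participant will not yet have experience with which to rate the program".

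**What is analysed.** Section 11.2 states every primary and secondary hypothesis as a between-site difference in change from baseline to 6 months.

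**The concern.** A between-site contrast of changes is interpretable only if baseline stands in a similar relation to program exposure at both sites. If program content raises DKQ or PAM-13 scores, whatever a patient receives before baseline is built into the baseline score and subtracted from that site's measured gain. The plan lets this happen in different ways at the two sites. Route-2 patients at One Hope have already had a provider visit and an exit interview. CDE-UNMH patients may have attended classes while their own screening and their social support's screening were being completed.

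The planned adjustment does not address this. The propensity variables named in Section 11.1 are sex, age, language, education, nativity and insurance, and none of them carries information on when baseline fell relative to exposure. The six REDCap instruments described in Section 9.2 (contact, demographic, survey, BMI, A1c, cortisol) are not described as holding the date of first program activity or any contacts before baseline. The program inventory collects sign-ups, no-shows and attrition, but as a description of each program. As written, the plan would not show afterwards how large the problem had been.

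**Working it through.** **Step 1: the passages side by side.**

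| | CDE-UNMH | One Hope |
|---|---|---|
| Approach (3.1) | At registration | Call before the visit; exit interview after the visit; flyer at no fixed time |
| Certain program contact before baseline | None stated | Route 2: doctor visit and exit interview |
| Possible program contact before baseline | Classes, if scheduling runs late | Further visits or activities, if scheduling runs late |
| Window for baseline | None | None |

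Route 2 combined with Section 2.2 contradicts the premise in Section 9.2 that participants lack program experience at baseline. A strict reading of the Section 3.1 exclusion would remove route-2 patients, yet the same section recruits them. Either reading leaves passages to reconcile.

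**Step 2: reproduce the plan's power.** Inputs from Section 11.2: n = 96 per site, DKQ difference 2.2, SD 3.8, two-sided alpha 0.025.
- Standard error = 3.8 × √(2/96) = 0.548.
- Noncentrality = 2.2 / 0.548 = 4.01, with 190 degrees of freedom.
- Noncentral-t power = 95.9%, against the stated 96%. It reproduces.

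**Step 3: an illustrative shift from late CDE-UNMH baselines.** The documents give no delay, no expected DSMS gain and no dose-response, so all three are assumed.
- Nine hours over six weeks is 9/6 = 1.5 h per week. A baseline two weeks into the course comes after 3/9 = one third of the content.
- Assume gain proportional to hours and a true DSMS gain of 3 DKQ points (range 1.5 to 4.5). The loss is 3 × 1/3 = 1.0 point (0.5 to 1.5). It applies to the site mean only if every CDE-UNMH patient is that late.
- With no true difference, the same noncentral-t calculation gives these rejection rates against a nominal 2.5%:

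| Mean shift (DKQ points) | Rejection rate |
|---|---|
| 0.25 | 4.0% |
| 0.5 | 9.2% |
| 1.0 | 33.4% |
| 1.5 | 68.3% |

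**Step 4: an illustrative shift in the other direction, from One Hope baselines after a visit.**
- A mean loss of 1.0 point leaves 2.2 − 1.0 = 1.2, with power 47.3%. If only a third of One Hope patients came by route 2, each would have to lose 1.0 / (1/3) = 3.0 points, which exceeds the whole planned difference.
- A mean loss of 0.25 leaves 1.95, with power 90.2%.
- A second parametrisation lets a share s of One Hope patients each lose a fraction f of the planned difference: 2.2 × (1 − s·f). With s from 1/3 to 1 and f from 10% to 50%, the difference runs from 2.13 to 1.10 and power (normal approximation) from 95% to 41%.

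If program content raises scores, the step 3 mechanism favours CCM and the step 4 mechanism favours DSMS. They may partly cancel. Nothing in the documents fixes the net sign.

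**The case against.** The strongest reply is that the plan already guards against prior exposure. The new-entrant condition and the bar on people already participating are real eligibility rules, and the stated reason for the bar is to protect the data collection schedule. Every route-2 patient is still screened against them. An established clinic patient with a new diagnosis can fairly be called new to the diabetes program. At CDE-UNMH the invitation travels with the class schedule, which suggests contact before the first class. Some provider contact before baseline is unavoidable at both sites, because patients must be identified by a provider, and differing entry points are part of comparing existing programs. All of this stands. It limits prior exposure, but it does not say when baseline must occur or what counts as participation.

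Three stronger readings are tempting, and the documents do not support them.
- A reader might infer that the change scores definitely measure different things. Only one of three One Hope routes is explicitly after a visit, its share is unknown, and late CDE-UNMH baselines are possible but not established.
- A reader might infer that people who never start a program can enter only through CDE-UNMH registration, which would depress the DSMS gain. One Hope route 1 also recruits before any visit, so never-starters can enter at both sites. The intention-to-treat and per-protocol comparison in Section 13.3, though loosely specified and offered for missing data, also bears on non-attendance.
- A reader might take the 33%, 68% or 47% figures as estimates. They need large average shifts across a whole site and rest on assumed inputs.

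**Conclusion.** The point holds in a limited form. The entry events differ by site, the exit-interview route conflicts with the plan's own premise of no program experience at baseline, and no rule or window orders baseline relative to the first class or visit. Comparability of the 6-month contrasts is therefore not assured. The effect could be trivial (0.25 point: 4.0% false positives or 90% power) or serious (1.0 point: 33% or 47%). Which applies depends on the route-2 share, the delay after class 1 and the gain made before baseline, none of which the documents give. No sample-size figure changes. It should be fixed, with medium confidence in its importance, because the planned propensity strata cannot remove the bias and the information needed to measure it is not specified for collection.

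**What to change.** In Sections 3.1 and 9.2, carried through to the repeated text in Section 23:

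1. Define newly entering and already participating at each site in terms of visits, classes or activities, and reconcile the One Hope description in 2.2, the eligibility rule and exit-interview route in 3.1, and the no-experience premise in 9.2.
2. At CDE-UNMH, require the baseline visit before the first class.
3. At One Hope, limit route 2 to a first diabetes-related visit, with baseline before any further program activity and within a fixed window (14 days, for example).
4. Record in REDCap the entry route, registration date, date of first attended activity and all program contacts before baseline.
5. Pre-specify two sensitivity analyses of the 6-month contrasts: one in patients with no program contact before baseline, which excludes route-2 patients, and one by entry route.

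These changes do not create an identical time zero: route 2 still starts after its index visit, and the report should say so. The cost is protocol wording, a few date fields and tighter scheduling. Some interested patients who cannot be seen in time will not be enrolled, and the sensitivity analyses will have fewer patients than the main one.
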